### ***Maximum earnings***

The maximum cash value of tangible incentives awarded to participants who remain continuously abstinent from all tested drugs will be approximately \$400 per subject. Actual payout is expected to average \$200 per subject or less, depending on the percentage of drug-free urines submitted.

## **12 ROLE OF COUNSELORS IN THE PROTOCOL**

It is the intent of the protocol to involve counselors wherever possible in order to provide additional support for participation and success of their study clients. Specific roles will be determined at individual CTP's. Among the possible roles are the following:

- Witness the informed consent procedure whenever possible.
- Include study urine testing results in clinical feedback and treatment planning
- Be present at recovery picks whenever possible
- Receive regular reports on client progress in the study
- Encourage clients to continue providing urine samples and to remain abstinent from all chemical substances during treatment
- Suggest tangible incentives for the cabinet.
- After appropriate training, operate the incentive program in order to provide backup coverage to RA's
- Work with clients to build life-style changes during periods of abstinence

- Provide suggestions regarding very low or no-cost incentives that may be implemented after the study ends.

### **13 FOLLOW-UP PROCEDURES**

Follow-ups will be conducted at 1, 3 and 6 months after study intake on an intent-to-treat sample of those who were randomized into study conditions. A brief assessment battery will be administered (see below) and a urine collected. Participants who complete these procedures will receive compensation at a rate of \$25 for each interview.

#### **Successful follow-up will require active subject tracking procedures.**

Contact information will be obtained at intake- names, addresses and phone numbers of 3 people who “will know where we can reach you”.

A reminder letter will be sent two weeks prior to scheduled interview requesting the participant call the office.

If person fails to call prior to scheduled day, contacts are telephoned repeatedly in an attempt to talk to the participant and messages are left for the participant to call or come in.

If no contact has been made by the scheduled date, then additional letters are sent to contact addresses and attempts to contact by telephone continue as well and additional information sought as to their whereabouts.

Individuals who have moved or have been difficult to contact may be interviewed over the phone. At that time, those who still reside in the area should be reminded that they can get their money if they come in to give a urine sample. This often results in an in-person contact.

These procedures have resulted in 95% interview completion rates.

### **14 STUDY ASSESSMENT BATTERY**

A battery of information will be collected at intake and at each follow-up contact. Intake battery will include the ASI Lite, Methadone treatment information, DSM IV Checklist, Services Utilization Report, Health Risk Behavior Survey, Gambling behavior survey and Brief Symptom Inventory. Shown below is the information to be collected in CRF's; information to be collected at intake only is so indicated.

#### ***Demographics*** (intake only)

Age, Gender, Race, Educational attainment, Marital status,

#### ***Methadone Treatment Information***

Methadone dose at study entry, Days in treatment at study entry,  
Methadone dose on last day of study participation

**DSMIV Checklist** (intake only) To characterize drug dependence profile.

**Contact information** (intake only)

Names, addresses and phone numbers of 3 people who will know where to find you and who we can contact to get messages to you.

**Services Utilization Report** (administered at intake, 3 and 6-month follow-ups only)

Treatment episodes in past 3 months

days of methadone maintenance

days of outpatient drug-free

days of residential treatment

days of outpatient detoxification

days of residential detoxification

Number of visits to an emergency room

**Recent drug use**

Urine testing:

Test cup result (opiates, cocaine, amphetamine, methamphetamine); breathalyzer reading.

Self-report: Days of use in the last 30 (from ASI lite)

opiates, cocaine, methamphetamine, alcohol, marijuana, sedatives

**HIV status** (intake only; note that clinics may be exempted from asking this question if local laws require reporting)

Positive, negative, don't know

**HIV risk exposure** (12-item HIV Risk Behavior Survey)

**Employment** (from ASI lite at enrollment or follow-up CRF)

Current employment status (full time; part time)

Days of work in the past 30

\$ earned for work in past 30

**Criminal activity** (from ASI lite at enrollment or followup-CRF)

Days of criminal activity in past 30 (drug dealing included)

Money earned for criminal activity in past 30 days

**Medical, family/social and psychiatric status** (ASI lite; intake only)

Days troubled by problems

**Gambling behavior**

Days spent money on gambling in past 30 (state lottery included)

Amount of \$ spent on gambling in past 30 days

*Psychiatric symptoms:* Brief Symptom Inventory (BSI)

## **15 OTHER PRE-STUDY AND DURING STUDY DATA TO BE COLLECTED**

### **15.1 Pre-study client retention and drug use**

Research staff will be charged with obtaining from clinic records information about overall clinic retention rates during the 6 months prior to study start. When possible, information about drug use profiles of entering clients will also be obtained in order to calculate stratified retention rates by drug use characteristics. This information will be used to determine whether overall clinic retention rates change over time as research is introduced.

### **15.2 Counseling utilization**

The research assistant, in collaboration with project coordinator and clinic staff, will be charged with setting up a system to track counseling utilization. The data desired is number of individual (15 minutes or more) and group counseling contacts per week for each study subject. Ideally, the clinic will already have a system for tracking this utilization data. In cases where a utilization tracking system is not currently in place, models will be suggested based on systems used in other participating CTP's.

## **16 ANALYSIS PLAN**

This section enumerates outcome measures and presents the statistical approaches that will be used to describe the data set and test study hypotheses.

### **16.1 Primary during-study outcomes**

Because the intervention targets stimulant drug use, the most sensitive measures for detecting intervention effects are likely to be measures of stimulant drug use observed during treatment. Therefore, two primary outcome measures will be defined:

- a) Percent of submitted urines cocaine, amphetamine and methamphetamine-free
- b) Longest duration of abstinence from primary target drugs (cocaine, amphetamine, methamphetamine, alcohol)

### **16.2 Secondary during study outcomes**

A variety of additional outcome measures will be collected during treatment and analyzed for between-group differences. These measures include:

#### **Retention**

Time from initial intake until last face-to-face contact censored at 12 weeks

### **Urinalysis**

Percent of scheduled urines submitted during 12 week study period  
Percent of breathalyzer tests reading 0.01 or higher  
Percent of submitted urines free of opioids and marijuana  
Longest duration of totally drug-free testing

Percent of patients achieving 4 and 8 weeks of abstinence:

- a. from primary target drugs
- b. from all tested drugs

### **Counseling utilization**

Total number of group and individual sessions received  
Mean number of group and individual sessions per week during weeks of participation

## **16.3 Follow-up outcomes**

The primary follow-up outcome is abstinence from stimulant drugs (cocaine and methamphetamine in the intent-to-treat sample at 1, 3 and 6 month follow-up time points.). Abstinence is defined as no stimulant use reported in the past 30 days and a stimulant negative urine. In addition, percent of stimulant negative urines alone will be used as an outcome measure at these time points.

Additional outcomes derived from urine testing and ASI interviewing data obtained at each follow-up time point include:

Percent of patients abstinent (negative urine/breath test and no reported use in the past 30 days) from alcohol, from opiates, from marijuana, and from all targeted drugs of abuse.

Days of use in the past 30 for each drug and for alcohol  
Days of criminal activity in the past 30 days  
Days paid for work in the past 30 days  
Days spent money on gambling in past 30 days  
HIV risk exposure score  
Psychiatric symptom score(s)

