## **8 STUDY PARTICIPANTS**

### **Inclusion criteria:**

1. Recent admission to an opioid substitution (methadone maintenance) CTP.
  - Completed at least 4 weeks of maintenance at time of study entry
2. Evidence of cocaine or methamphetamine use
  - Minimum of one documented positive urine within 2 weeks of study entry.
  - For those exiting a controlled environment, any stimulant use within two weeks of entering the controlled environment

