## **11 STUDY PROCEDURES**

## **11.1 Timeline**

A time and events schedule of study activities is shown in Table 1. An outline of the study timeline follows:

1. Determination of study eligibility and randomization
2. Study intervention: 12 weeks
3. Follow-up evaluation: 1, 3 and 6 months after study intake.

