**Table 1. Motivational Incentives Time and Events Schedule**

Activity	Screening	Enrollment	Treatment (week)												Follow-up (months)
			1	2	3	4	5	6	7	8	9	10	11	12	
Standard treatment 															
Informed consent	X														
Urine test (test-cup)	X	X	2X	2X	2X	2X	2X	2X	2X	2X	2X	2X	2X	2X	
Alcohol Breathalyzer		X	2X	2X	2X	2X	2X	2X	2X	2X	2X	2X	2X	2X	X
Incentive Drawing		X	2X	2X	2X	2X	2X	2X	2X	2X	2X	2X	2X	2X	
Usual care urine testing 		X		X		X		X		X		X		X	X
Drug-use 	X	X				X								X	X
BSI		X				X								X	X
HIV risk exposure		X				X								X	X
Gambling behavior		X				X								X	X
Employment status 		X				X								X	X
Criminal activity 		X				X								X	X
HIV status		X													
Demographics; DSMIV checklist		X													
Contact information		X													
Treatment history		X												X	X
Counseling utilization 															
Follow-up urine testing						X								X	X

1. Occurs during the entire 12-week study.

2. Performed on alternative weeks during the treatment. May be started in week 2 and performed in weeks 4, 6, 8, 10, and 12.

3. Documented throughout the treatment according to participation.

4. From ASI at enrollment and follow-up CRF at other time-points

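### The month-1 follow-up sits in treatment week 4, so its 30-day look-back reaches about 2 to 8 days before intake and scores some participants who stopped at entry as not abstinent

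*Protocol*

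**What the plan says.** Four parts of the protocol bear on this.

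- **Outcome.** Section 16.3 names abstinence from stimulants as the primary follow-up outcome ("cocaine and methamphetamine in the intent-to-treat sample at 1, 3 and 6 month follow-up time points") and sets the rule: "Abstinence is defined as no stimulant use reported in the past 30 days and a stimulant negative urine". Both parts must be met. The same section adds the stimulant-negative urine alone as a further outcome at the same time points.
- **Self-report item.** Section 14 records it as "Self-report: Days of use in the last 30 (from ASI lite"). It does not ask about use since study entry.
- **Timing.** Section 11.1 gives "Follow-up evaluation: 1, 3 and 6 months after study intake", and Section 13 repeats it: "Follow-ups will be conducted at 1, 3 and 6 months after study intake on an intent-to-treat sample". Neither gives a visit window. Table 1 ("Motivational Incentives Time and Events Schedule") marks the row "Follow-up urine testing" at week 4, week 12 and the follow-up column. The drug-use, BSI, HIV risk, gambling, employment and criminal-activity rows are also marked at week 4.
- **Eligibility.** Section 8 requires recent stimulant use: "Minimum of one documented positive urine within 2 weeks of study entry". Participants leaving a controlled environment can qualify on use before they entered it.

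**The concern.** Week 4 ends before 30 days have passed since intake. Read with Table 1, the month-1 outcome therefore asks partly about days before randomisation, and those are days in which the trial selects for stimulant use. The randomised intervention cannot change what happened then. Someone who used just before intake, stopped on entry and gave a negative urine at week 4 would have to report use truthfully and would be scored as not abstinent.

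At stake is the month-1 reading of the primary follow-up outcome, which Section 17.2 turns into a primary hypothesis. Section 16.4 proposes GEE for outcomes measured at several time points and considers that treatment effects may decay. A month-1 result that is artificially low, beside unaffected results at months 3 and 6, could dilute a pooled effect and hide early decay.

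**Working it through.** The protocol states no figure to reproduce here. The check is calendar arithmetic, followed by an illustration.

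**1. Is week 4 a misread column?** The usual-care urine row of Table 1 falls in weeks 2, 4, 6, 8, 10 and 12, which agrees with footnote 2. The columns are therefore aligned and the week-4 marks can be taken as they stand.

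**2. Overlap.** Take intake as day 0. Under Section 11.2 intake and randomisation normally share a day. An interview on day d looks back over days d − 30 to d − 1, so the number of pre-intake days is max(0, 30 − d).

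| Interview day | Look-back starts | Pre-intake days | Share of 14-day eligibility window | Intake day included |
|---|---|---|---|---|
| 22 | −8 | 8 | 8/14 = 57% | yes |
| 24 | −6 | 6 | 43% | yes |
| 26 | −4 | 4 | 29% | yes |
| 28 | −2 | 2 | 2/14 = 14% | yes |
| 30 | 0 | 0 | 0% | yes |
| 31 | 1 | 0 | 0% | no |

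Counting intake as day 1 adds one pre-intake day to the week-4 rows.

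**3. Other time points.** At week 12 (days 78 to 84) the look-back starts on day 48 to 54. At month 6 (about day 182) it starts on day 152. Neither reaches intake.

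**4. Who is rescored.** The score changes only for a participant who meets all three conditions:
- used on an overlap day or the intake day;
- did not use again before the visit;
- gave a negative urine at the visit.

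Anyone who uses after intake and within the look-back fails anyway. Anyone whose last use fell earlier in the two weeks, or who entered through the controlled-environment route without use in the overlap, can still pass.

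**5. Direction.** Let f be the share of truly abstinent participants who are rescored, taken as equal in both arms. Abstinence p becomes p(1 − f) in each arm, so the difference shrinks by the factor 1 − f. The relative risk stays the same but is estimated less precisely.

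**6. Illustration only.** The protocol does not give f, nor month-1 abstinence rates. Borrow the 28.5% and 16.3% that Section 9 quotes (drug-negative urines in months 5 and 6 of a cited study), and the planned 200 per group. With Δ = p1 − p2 and p̄ their mean, power = Φ{[Δ√n − 1.96√(2p̄(1 − p̄))] / √(p1(1 − p1) + p2(1 − p2))}.

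| f (assumed) | Rates | Difference | Power |
|---|---|---|---|
| 0 | 28.5% vs 16.3% | 12.2 points | 84% |
| 0.10 | 25.7% vs 14.7% | 11.0 | 78% |
| 0.25 | 21.4% vs 12.2% | 9.1 | 69% |
| 0.50 | 14.2% vs 8.2% | 6.1 | 49% |
| 0.75 | 7.1% vs 4.1% | 3.0 | 26% |

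The range is wide because f is unknown. The table shows direction and does not estimate the loss.

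**7. Count items.** Gambling, crime and work are counted in days or money over 30 days. At week 4 they share 2/30 to 8/30 of their window (7% to 27%) with days before intake. That dilutes a change from baseline mildly; it is not an all-or-nothing failure.

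**The case against.** **The text says one month, and week 4 is only a nominal slot.** Table 1 has weekly columns for the treatment phase and treats week 12 as month 3 in the same way. At day 30 only the intake day remains in the look-back, and at day 31 nothing does. This stands as a limit: the defect comes from Table 1's placement together with the absence of a visit window. It does not remove the point, because a site that follows Table 1 will interview before day 30. A window may exist in an operations manual or analysis plan that is not shown. But a count of days used in the last 30 cannot be split afterwards into days before and after intake.

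**The error is balanced and partly covered.** This stands. Pre-entry use precedes randomisation, and intake stimulant status is a stratification factor (Section 11.2). The urine-only outcome has no look-back, and the two during-treatment primary outcomes in Section 16.1 do not use self-report.

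**A stronger reading that a reader might infer.** Section 9 expects 20 to 35% cocaine-negative urines in eligible methadone patients. A reader could conclude that 65 to 80% of participants cannot meet the month-1 definition, and that a true 15-point effect would show as 15 × 0.20 = 3 to 15 × 0.35 = 5.3 points. The protocol does not support this. The 20 to 35% is a rate of negative urines in cited studies, not the share of participants negative at intake. How long a urine stays positive after use is not stated. Many of those who cannot pass would fail through later use anyway. The shrinkage also depends on where the effect lies. Assume 30% are negative at intake: an equal 15-point effect would show as 0.30 × 15 = 4.5 points. With 30 points in that group and about 8.6 in the rest (0.30 × 30 + 0.70 × 8.6 ≈ 15), it would show as 0.30 × 30 = 9.

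**Conclusion.** The point holds in a limited form. If Table 1 is followed, the month-1 look-back takes in about 2 to 8 pre-intake days plus the intake day, and some participants who stopped at entry and stayed abstinent are scored as not abstinent. Measured month-1 abstinence is lowered in both arms and the absolute difference tends to shrink. The size cannot be estimated from the protocol.

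This rests on three things: week 4 read as days 22 to 28 with intake as day 0, truthful self-report, and no visit window set elsewhere. The protocol does not support saying that pre-entry use decides the result for most participants, or that either arm is favoured. One of three time points of the primary follow-up outcome is affected. It is worth correcting before data collection, and it does not threaten the trial's main efficacy comparison.

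**What to change.** Reconcile Table 1 with the text. State in Sections 11.1, 13 and 16.3 that the month-1 follow-up takes place no earlier than day 31 after intake, and move the week-4 follow-up marks in Table 1 to week 5 with that lower limit. The same 30-day item then serves at all three time points, and the overlap also disappears for gambling, crime and work. The cost is a visit a few days later; participants are expected twice weekly at that stage in any case (Section 11.4).

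If the visit has to stay in week 4, add one item to the follow-up CRF on stimulant use since the day after intake. Score month-1 abstinence on that item plus the negative urine, and say so in Section 16.3. The cost is a slightly different definition at month 1 from months 3 and 6, which any repeated-measures analysis would have to acknowledge. The first option is preferable for that reason.

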## **16.4 Data analysis plans**

### **Descriptive statistics**

Frequencies will be run and examined for evidence of sparseness for categorical data and for non-normality (using plots, examination of skewness, kurtosis etc.) for continuous variables. Where sparseness exists in categorical variables, we will collapse as necessary to produce sufficient cell sizes. Where non-normality is evident, variables may be transformed. Outliers may be recoded or omitted if necessary. Wherever the statistics that are proposed below assume normality, we recognize that non-parametric alternatives may be necessary.

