### **11.4 Sample collection and testing procedures**

#### ***On-site urine testing***

Study participants will be expected to give urines twice weekly throughout the 12-week study (total of 24 urines including intake urine). It is recommended that the first urine be collected on Monday and the second on Thursday.

Clients who are absent on the day of scheduled urine collection can give a sample the next time they come to the clinic. Any two samples given within a week on non-consecutive days will qualify for participation in incentive procedures. Special arrangements for urine collection on unscheduled days can be arranged for individuals who have excused absences or emergencies.

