### **Continuous and dichotomous summary variables**

For summary variables using continuous data (e.g. percent of negative urines; longest duration of abstinence), we will use t-tests for simple analyses and multiple regression if it is necessary to control for baseline or other covariate differences. For summary variables using dichotomous data (e.g., percent of patients achieving 30-day abstinence at follow-up or achieving 4 or 8 weeks of abstinence during treatment), we will use chi square with relative risks and 95% confidence limits for simple comparison of treatment groups. If it is necessary to control for covariates, logistic or Poisson regression will again be used.

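### The open permission to recode or omit outliers reaches both bounded during-study primary outcomes and can bias the treatment effect in either direction

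*Protocol*

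**What the plan says.** Section 16.4 opens with data screening under Descriptive statistics. Continuous variables are inspected for non-normality, and three remedies follow. The first is "Where non-normality is evident, variables may be transformed". The second is "Outliers may be recoded or omitted if necessary". The third is "Wherever the statistics that are proposed below assume normality, we recognize that non-parametric alternatives may be necessary". The screening therefore prepares data for the tests that come after it and is not confined to descriptive tables.

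Those tests include the following, under Continuous and dichotomous summary variables: "For summary variables using continuous data (e.g. percent of negative urines; longest duration of abstinence), we will use t-tests", with multiple regression if covariates are needed. The two variables named there are the two primary during-study outcomes of section 16.1. One is "Percent of submitted urines cocaine, amphetamine and methamphetamine-free". The other is the longest duration of abstinence from the four primary target drugs.

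Section 11.4 fixes the testing schedule at a "total of 24 urines including intake urine" over 12 weeks. Section 11.5 says that the escalating schedule of picks is meant to sustain long periods of abstinence.

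**The concern.** Neither primary outcome is an open-ended measurement that can drift to implausible values. Percent negative lies between 0 and 100. Longest abstinence cannot exceed the 12-week study. Both are built from single positive or negative tests, so 100% negative or a 12-week run is a possible and usually genuine result. It is also the result that the intervention is designed to produce. If one test record is wrong, the remedy is to correct that record, not to drop the person.

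Omitting a participant because the summary value looks extreme selects on the outcome after randomisation, so the arms are no longer the groups that were randomised. The permission is tied only to necessity, so the choice of rule, and with it the direction of the bias, is left to judgement. What is at stake is the size of the primary effect estimate and, under some rules, the type I error.

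**Working it through.** **Stated figures.** The protocol gives no figure for the outlier rule, so there is none to reproduce. The check asks what common rules would do to the two outcomes at the protocol's own rates.

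**Inputs from the protocol**
- 200 per group; two-sided alpha 0.05 (section 9)
- 24 scheduled urines (section 11.4)
- Expected cocaine-negative rate 20-35% in eligible methadone patients; detectable difference 10-15 points; rates of 16.3% v 28.5% behind the 130-per-group calculation (section 9)

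**Assumed inputs**
- Each participant has a personal probability of a negative test, logit-normal with SD 2 or 3 on the logit scale.
- Control/incentive means are 16.3/28.5%, 20/35% and 35/50%.
- Tests are independent given that probability, and none is missing.
- Percent negative = negatives / 24. Longest abstinence in weeks = longest negative run / 2.
- Rule: omit values outside Q1 - 1.5 IQR to Q3 + 1.5 IQR, with quartiles taken from both arms together (pooled) or from each arm (within-arm).

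**Plausibility of the spread.** The protocol gives no SD. If 130 per group came from a two-means formula, n = 2(1.960 + 0.842)² SD² / 0.122², then SD = 0.351. In the simulations the between-person SD of the probability runs from 0.21 to 0.31 at logit SD 2 and from 0.26 to 0.37 at logit SD 3. The wider setting is closer to the implied value.

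**Longest abstinence, pooled rule** (average numbers removed of 200 per arm; cut = 1 - after/before)

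| Logit SD | Means, % | Removed, control | Removed, incentive | Ratio | Difference, all kept (wk) | After omission (wk) | Cut |
|---|---|---|---|---|---|---|---|
| 2 | 16.3/28.5 | 11.0 | 27.4 | 2.5 | 0.68 | 0.26 | 61% |
| 2 | 20/35 | 11.7 | 31.9 | 2.7 | 0.92 | 0.34 | 63% |
| 2 | 35/50 | 9.4 | 23.2 | 2.5 | 1.20 | 0.64 | 47% |
| 3 | 16.3/28.5 | 14.9 | 32.9 | 2.2 | 0.87 | 0.23 | 73% |
| 3 | 20/35 | 14.0 | 33.4 | 2.4 | 1.15 | 0.38 | 67% |
| 3 | 35/50 | 13.4 | 28.1 | 2.1 | 1.40 | 0.75 | 46% |

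Power falls less than the estimate, because omission also shrinks the spread. At 20/35% with logit SD 3 it goes from 0.99 to 0.91.

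**Percent negative, within-arm rule**

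| Logit SD | Means, % | Removed, control | Removed, incentive | Difference, all kept (points) | After omission (points) |
|---|---|---|---|---|---|
| 2 | 16.3/28.5 | 15.0 | 0.8 | 12.3 | 16.7 |
| 3 | 16.3/28.5 | 25.0 | 0.6 | 12.2 | 20.5 |
| 2 | 20/35 | 11.7 | 0 | 15.1 | 19.1 |
| 3 | 20/35 | 18.1 | 0 | 15.1 | 21.8 |
| 2 or 3 | 35/50 | 0 | 0 | 14.9 | 14.9 |

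Here the bias runs the other way. The pooled rule on the same outcome at 16.3/28.5% (logit SD 3) removes 6.7 control and 16.6 incentive participants and lowers the difference from 12.2 to 8.7 points. The same data can therefore give 8.7, 12.2 or 20.5 points, depending on a choice that the sentence leaves open. At 35/50% neither rule removes anyone on percent negative.

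**No true effect.** With beta-distributed probabilities (mean 20%, SD 0.30) in both arms, the within-arm rule on longest abstinence gives a two-sided type I error of about 28%, against about 7% with everyone kept. The pooled rule does not raise it (about 6%).

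**The case against.** The strongest reply is that the sentence is permissive and general. It says that outliers may be handled, not that they will be. It covers every continuous variable, including dollars earned or spent on gambling, where a heavy tail is a real nuisance. Outlier definitions are commonly left to a statistical analysis plan, which is not at hand. All of this is fair, and the lack of a threshold is not the point raised here. What stands is that the protocol itself grants permission to omit values and does not exempt the primary outcomes.

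Four stronger readings are tempting, and the document does not support them.

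- A reader might infer that the rule will mainly delete successful incentive participants. The protocol does not say who would be removed. Within-arm rules can remove mainly controls, under a beta model pooled removals are often about equal between arms, and for percent negative at 35/50% the rules examined remove nobody.
- A reader might infer that outliers would be judged with arm known. The protocol is silent on this. It only does not require masking.
- A reader might say that intent-to-treat, as declared, is breached. The wording in section 13, "on an intent-to-treat sample of those who were randomized into study conditions", describes the follow-up interviews, and the primary follow-up outcome is dichotomous. The objection for the during-study outcomes is selection on outcome after randomisation, which needs no such declaration.
- A reader might hold that no in-range value can be wrong. A mislabelled or mis-entered test can produce one, so correction of verified errors must remain possible.

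**Conclusion.** The concern holds in this form: an open permission to omit or recode outliers reaches both bounded primary outcomes, where extreme values are usually genuine, and using it can dilute or inflate the effect. Under the assumed logit-normal models, pooled omission cuts the difference in longest abstinence by roughly half to three quarters, and within-arm omission can raise a 15-point difference in percent negative to 19-22 points. These figures show what the permission allows. They are not forecasts for this trial, because they rest on assumed distributions, complete testing and assumed outlier rules, and only omission was simulated, not recoding. The defect itself does not depend on any one of these models. The sentence should be changed, but the protocol does not show that any participant will in fact be removed.

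**What to change.** Replace the outlier sentence in section 16.4 with: *In the primary analyses all valid values of randomised participants are kept; only verified data errors are corrected, without knowledge of study arm. Non-normality is handled by the transformation or non-parametric methods named here; any analysis that recodes or omits outliers is a pre-specified sensitivity analysis.*

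No new test is needed, since the same paragraph already offers methods that keep every participant. Participants know their assignment, but whoever verifies a suspect test record can still be kept unaware of it. The cost is a short text change, slightly more variable estimates and, if wanted, one extra sensitivity analysis.
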